The purpose of this study is to investigate the effect of short-term water restriction on blood pressure responses to various maneuvers in old adults. A secondary purpose is to investigate if daily physical activity levels affect blood pressure control in young adults. Under various hydration states, the body compensates by managing blood electrolyte and body water levels to maintain blood volume and blood pressure balance. This compensation is thought to be diminished with aging. Previous studies have shown that dehydration status impairs how our body controls the sympathetic nervous system and blood pressure under resting conditions. The purpose of this study is to assess how hydration (mild dehydration vs. normal hydration) status affects the blood pressure responses during different tests that stimulate the sympathetic nervous system in old adults. Handgrip exercise with arm cuff occlusion, the hand in cold water test, and a breath hold will be used to stimulate sympathetic responses. These tests will provide specific insight into how hydration status affects how our body controls blood pressure.

6. PROCEDURES

Describe all procedures involving human subjects for this protocol. Include copies of all surveys and research measures.

*If necessary. Seven-day physical activity monitoring may be done between earlier visits when possible based on scheduling.

Participants enrolled prior to February 2018, who have indicated they can be contacted for future research studies, will have the opportunity to undergo activity monitoring for seven days. They

will come in for two visits (one for pick-up, one for drop off) to obtain the activity monitor, wear it for seven consecutive days, then return it.

Total Visit Time Summary (up to 6 total visits: ~8 hours total time commitment for Old adults; and up to 4 total visits: ~5 hours total time commitment for Young Adults)

Old Adults: Following the participant's initial consenting visit (up to 30 minutes), the participant will return for a screening visit with the Nurse Managed Primary Care Center at STAR Campus, Newark, DE (approximately 1 hour). The next visit will be a familiarization visit (30 minutes), which will allow for the participant to practice the exercise trial that will be used during the study visits. Following the participant's familiarization visit, we will schedule two study visits separated by one week. Each study visit will require approximately 3 hours.

Young Adults: Participants will come in for a consent and screening visit (approximately 1 hour). Young participants will be screened by a member of the Cardiovascular Physiology Research Team at STAR Campus, Newark, DE. The next visit will be a familiarization visit (30 minutes), which will allow for the participant to practice the exercise trial that will be used during the study visits. Following the participant's familiarization visit, we will schedule one study visit that will require approximately 3 hours.

Hydration Protocols

Three days prior to each study visit old participants should follow instructions for consuming recommended sodium diet (2,300 milligrams). They will be assigned to a normal hydration and water restriction protocol for each of the two study visits, in a random order. Young adults will complete only a normal hydration protocol. The table below indicates the fluid intake participants will be asked to follow for each protocol by day. Participants will drink 23mL water per kg of body weight for the normal hydration condition, and 10mL water per kg bodyweight for the water restricted condition. Below is the intake plan for both conditions.

	Normal Hydration	Water Restriction
Day 1	54oz	54oz
Day 2	54oz	40oz
Day 3	54oz	24oz
Morning of Visit	8oz	Avoid fluids

*based on a 70kg (154lb) participant. This will be customized for each participant based on their body weight.

Water and food will not be provided to the participants, they will be given a water bottle with liquid measure marks to maintain the recommended water intake. They will be given information on how to correctly complete a food log while using instructions to avoid high dietary sodium. Participants will also be given a list of foods that are high in water content to avoid 24 hours prior to their study visit. They will be given a protective case and be instructed on how to operate the blood pressure cuff that they will wear for the 24 hours preceding each study visit. This blood pressure cuff will measure blood pressure every 20 minutes throughout the day and every 30 minutes during night time. A 3-day diet record will also be kept during the 3 days prior to data collection visits. Participants will also be instructed to avoid caffeine, alcohol, and moderate-to-vigorous (running, lifting weights, etc.) exercise 72 hours prior to their data collection visits.

Consent visit for old adults (30 min)

A laboratory member will explain the informed consent document to the participant. We will also answer any questions the participant may have. We will bring participants to the Nurse Managed Primary Care Center to schedule a screening visit.

Screening visit for old adults (1 hour)

Participants will be asked to avoid caffeine, alcohol, and exercise in the 24 hours prior to this visit. The following information will be obtained to confirm inclusion criteria are met: a complete medical history using a questionnaire, a PAR-Q (physical activity readiness questionnaire), height, weight, waist circumference, hip circumference, a resting electrocardiogram (10 self-adhesive electrodes will be placed on their chest), resting blood pressure, a body fat assessment, and a blood sample (obtained with a needle from a vein in the arm). If a participant answers “yes” to one or more questions on the PAR-Q they will be enrolled into the study on a case-by-case basis. The blood sample will be used to obtain an assessment of liver function, a lipid profile, a complete blood count, glucose, sodium, potassium, chloride, and kidney function. About 2 teaspoons (1.0 fluid oz.) will be sampled. All information will be reviewed by the Nurse Managed Primary Care Center and by the study investigators, and only those with no signs or symptoms of disease (example: chest pain, dizziness, or shortness of breath, etc.), blood pressure within specific limits, blood work within normal limits, and a resting electrocardiogram within normal limits, will be accepted into the study. Also, the medical history form and PAR-Q will be reviewed by the study investigators and Nurse Managed Primary Care Center to determine if the participant qualifies for the study. In addition, participants will be excluded if they are obese (body mass index greater than or equal to 30 kg/m²), if they use any tobacco products. For women, menopause will be confirmed prior to testing. All medications will be reviewed on a case-by-case basis by the Nurse Managed Primary Care Center and study investigators to determine eligibility for study participation. The investigator(s) will discuss the results of these tests with the participants, and upon their request, we will make copies of these results for them.

Combined consent and screening visit for young adults (1 hour)

A laboratory member will explain the informed consent document to the participant. We will also answer any questions the participant may have. Participants will complete a PAR-Q. Participants will be screened at the Cardiovascular Physiology Research Laboratory at the University of Delaware. This involves completing a medical history questionnaire, measuring resting blood pressure, height and weight. Investigators review all information and only those with no signs or symptoms of disease will be asked to participate (example: history of chest pain, dizziness, or unusual shortness of breath, etc.). Female participants will have a urine pregnancy test administered to ensure that they are not pregnant. Individuals taking hormonal contraceptives will be permitted to participate in the current study. Additional exclusion criteria include: if resting blood pressure is outside specific limits (systolic blood pressure 90-139mmHg and/or diastolic blood pressure 50-89mmHg), if hypotension is present (systolic blood pressure <90mmHg and/or diastolic blood pressure <50mmHg), a history of cancer, diabetes, or any other chronic disease; a history of any heart disease; hormone therapy; use of tobacco or nicotine products; or a body mass index greater or equal to 30kg/m². In the event that one of the test results is abnormal or a positive pregnancy test, they will be referred to their personal physician.

Familiarization & equipment pick-up visit (30 min)

All participants will come to the Cardiovascular Physiology Lab (STAR Campus Lab 128) for protocol familiarization. During the familiarizations, participants will practice a handgrip exercise and post exercise arm cuff occlusion trial to simulate a data collection visit. Participants will be provided with a special backpack designed to carry the plastic urine container and blood pressure monitor.

Experimental visit (3-hour visit)

Participants will arrive to the Cardiovascular Physiology Laboratory (STAR Campus Lab 128) fasted 4 hours. Participants will hand in the equipment backpack. The urine sample will be analyzed for salt content, as well as for the concentration of several hormones that control salt and water balance. Some of these analyses will be done immediately in the lab, and some of the urine sample will be stored in a freezer for future analysis. The participants name will not appear on the stored urine sample; rather, the sample will be coded with a number.

Urine Analysis

Upon arrival to the Cardiovascular Physiology Laboratory, participants will collect a spot urine sample during the same time they void prior to the start of the testing visit. This will be used to analyze hydration status and check pregnancy for pre-menopausal female adults. In the event of a positive test, they will be notified and be excused from further participation. We will also refer them to their personal physician.

Catheter Insertion & Blood Sample

A research nurse or [name] will place a catheter into the participants' dominant arm. We will insert one catheter into the dominant arm in retrograde fashion, leaving a small flexible tube in their vein. About 7.5 tablespoons (3.8 fluid oz.) will be sampled from the intravenous catheter (IV), and some of the blood will be stored in a freezer for future analysis of hormones that control salt and water balance in the body. Blood samples from the catheter placed in their dominant arm will be collected prior to handgrip exercise, immediately after handgrip exercise during post exercise arm cuff occlusion, and after cuff deflation. The catheter will be removed at the end of each study visit.

In the event a research nurse or [name] are unavailable, a lab member trained in phlebotomy will perform a baseline blood draw and we will miss the post exercise blood samples.

Measurements for neural circulatory control- Blood Pressure, Heart Rate, Respiration and Blood Flow Measurements

Blood pressure will be measured at the middle finger of the non-dominant hand, on a beat-by-beat basis. The finger pressure will be calibrated to brachial artery pressure according to the manufacturer's recommended calibration instructions before the protocol begins. Additionally, brachial blood pressure will be measured at rest and after exercise. A three-lead ECG will be used to measure heart rate, we will place 4 sticky pad electrodes on their shoulders (2) and stomach (2). Breathing frequency and depth will be measured by placing a respiratory band around their lower chest. An ultrasound probe will be used to measure blood flowing in their

upper leg (femoral artery). We will be measuring beat-by-beat blood pressure, heart rate, respiration, and blood flow continuously throughout the visit.

Microneurography

To assess acute sympathetic responses during exercise, we will directly record their nervous system activity at the peroneal nerve using the technique of microneurography. The peroneal nerve runs on the outside of the lower limb, near the fibular bone. The microelectrode will be inserted through the skin just below the knee. A reference microelectrode will also be inserted into the skin above the placement of the microneurography electrode. The insertion point will be determined by external electrical stimulation to elicit involuntary muscle twitches of the lower leg. When the nerve has been located, the electrode will be used to record nerve activity. The fine wire electrode will be removed following each study visit. [name], [name], or [name] will be performing the microneurography technique.

Figure 1: Example of fine wire electrode.

Tests of Sympathetic Reactivity

Isometric Handgrip Exercise and Post Exercise Ischemia

Participants will perform a handgrip exercise bout lasting 2 minutes at approximately 30%. Maximal handgrip strength of the dominant hand will be measured by having the subject squeeze the handgrip device as hard as possible three-five times. The highest value will be used as the maximum, and this will be used to calculate relative work rates of approximately 30%. In our experience, most participants perceived work rate during the handgrip exercise tends to be “moderate” to “moderately hard.” During the last 3 seconds of exercise, a cuff on their upper dominant arm will be inflated and will remain inflated for 3 minutes and 15s. The cuff will be deflated and data collection will continue during recovery for 2 minutes. During handgrip exercise, they will be encouraged to stay relaxed and to breathe normally, so as to not inadvertently dislodge the fine wire electrode from the nerve recording site. Dislodging the fine wire electrode does not pose any risk to the subject, but it does prevent us from obtaining a usable nerve recording. We will also use the Borg rating of perceived exertion (RPE) scale to determine how hard participants perceive they are working. Using the Borg scale, subjects will report an RPE between 6 and 20 during each minute during exercise.

Hand in Cold Water Test

A small bucket will be filled with a slurry ice and water mixture. The participant’s dominant hand will be submerged in the cold water for 2 minutes and data collection will continue during recovery for an additional 2 minutes.

Voluntary End-Expiratory Apnea

Participants will be asked to exhale all of the air from their lungs, then be asked to hold their breath for as long as they can (typically lasting 30s). After participants can no longer hold their breath, they will resume normal breathing.

Participants will be offered water to consume at the end of their data collection visit. Participants will leave with an accelerometer after the first (young adults) or second (old adults) experimental visit and return for a brief (≤ 5 minutes) visit to return the accelerometer.

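### Older adults' crossover: food is self-chosen before each visit and no use of the 3-day diet record to make the two periods alike is stated; have period-1 foods repeated before visit 2 (minor, cheap improvement)

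*Protocol*

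**What the plan says.** All of this is in Protocol section 6, Procedures.

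- **Design.** Older adults receive both hydration conditions, "for each of the two study visits, in a random order". On timing, "we will schedule two study visits separated by one week". For the other age group, "Young adults will complete only a normal hydration protocol".
- **Fluids.** The full doses are 23 mL/kg and "10mL water per kg bodyweight for the water restricted condition". The day-by-day table for a 70 kg person steps the restricted condition down from 54 oz to 40 oz to 24 oz, with nothing on the morning of the visit.
- **Food.** "Water and food will not be provided to the participants". Older adults are told to follow a 2,300 mg sodium diet for three days before each visit and are shown how to fill in a food log. "Participants will also be given a list of foods that are high in water content to avoid 24 hours prior to their study visit". Caffeine, alcohol and moderate-to-vigorous exercise are excluded for 72 hours.
- **Record.** "A 3-day diet record will also be kept during the 3 days prior to data collection visits". Nothing further is said about what is done with it.
- **Checks at the visit.** "The urine sample will be analyzed for salt content", along with hormones of salt and water balance, and a spot urine is used to assess hydration status.

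Section 15 lists a separate participant packet for each hydration condition. Neither is shown.

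**The concern.** The older adults' comparison is within person: the same participant mildly dehydrated and normally hydrated. Its strength is that whatever stays the same across the two periods cancels. Food does not automatically stay the same, and both food water and sodium act on the quantity being manipulated. The protocol recognises this by setting a sodium target and an avoid-list.

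Two consequences are possible. If food differs between periods for unrelated reasons, it adds within-person noise. If it differs because of the condition (participants know how much they are drinking, and someone drinking less may choose wetter food), it shifts the contrast. Random order balances period effects but does not remove a response to the condition itself. Urine measures and the record can reveal a difference afterwards. They cannot prevent it, and no later analysis can make two past diets match.

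**Working it through.** **Inputs.** Doses and the 70 kg fluid table come from section 6, Hydration Protocols; the one-week interval comes from section 6, Total Visit Time Summary. Conversion: 1 oz = 29.57 mL.

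**1. Reproduce the table.** Normal: 23 × 70 = 1,610 mL; 1,610 / 29.57 = 54.4 oz (table 54). Full restriction: 10 × 70 = 700 mL; 700 / 29.57 = 23.7 oz (table 24, Day 3). The table agrees with its doses. Day 2 is a step-down: 40 × 29.57 = 1,183 mL, and 1,183 / 70 = 16.9 mL/kg.

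**2. Planned contrast, set against food-water control.**

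| | Normal (oz) | Restricted (oz) | Difference (oz) | Share | Avoid-list in force |
|---|---|---|---|---|---|
| Day 1 | 54 | 54 | 0 | 0% | no |
| Day 2 | 54 | 40 | 14 | 27% | no |
| Day 3 | 54 | 24 | 30 | 58% | about the whole day |
| Morning | 8 | 0 | 8 | 15% | yes |
| Total | 170 | 118 | 52 | 100% | |

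In volume, 52 × 29.57 = 1,538 mL, of which Day 2 is 14 × 29.57 = 414 mL. The 24-hour list covers roughly the part where 38 of 52 oz (73%) arises. Day 2 is the one day with a fluid difference and no food-water rule.

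**3. Sodium.** The same target applies on all three days before both visits. A target steers the average level; it does not make one person's two periods equal.

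**4. Is repetition of foods asked for?** The shown protocol contains no such instruction, and no statement that the record is reviewed or compared across periods.

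**5. Illustration of the noise (assumptions mine).** The protocol gives no alpha, power or standard deviation. Take two-sided 0.05, 80% power, 40 pairs, and let f be the share of within-person difference variance that comes from diet and would be removed by matching. The detectable standardised difference is (1.960 + 0.842) / √40 × √(1 − f): 0.443 at f = 0, 0.420 at 0.1, 0.396 at 0.2 and 0.371 at 0.3. Nothing in the documents says where f lies, and it may be close to zero.

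**6. Feasibility of the fix.** Visits are 7 days apart and preparation takes 3 days, so period-2 Day 1 falls 7 − 3 = 4 days after visit 1. A copy handed over at visit 1 is in time.

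**The case against.** The case on the other side is substantial.

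- **Silence is not misuse.** A reader might infer that the record is collected and then left unused. The protocol supports only the weaker statement that no such use is given. The unseen packets are a natural home for an instruction to repeat meals, and use of the record in the analysis could properly sit in an analysis plan. This stands, and limits the point to what the shown text says.
- **Diet is already controlled.** A reader might infer that food is uncontrolled. It is not: the sodium target, the avoid-list and the 72-hour exclusions apply before both visits, and urine measures show the hydration state reached. What remains is Day 2 food water and variation around the sodium target.
- **No size is documented.** One could assume a 150–250 mL water-rich serving that differs between conditions and infer a shift of 10–16% in the planned contrast (150 / 1,538 and 250 / 1,538), in either direction. That serving appears nowhere in the documents, zero is equally compatible with them, and a share of planned intake is not an effect on hydration or blood pressure. It cannot be reported as a bias.
- **Copying can carry a fault forward.** Someone randomised to restriction first may eat differently because of it, and would then repeat that diet under normal hydration. A period-1 diet over the sodium target would be repeated too. The second problem is met by replacing items that broke a rule; the first remains as a residual drawback, although the person's two periods would still be more alike.

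**Conclusion.** The point holds as a minor, inexpensive improvement to trial conduct. On the shown text, nothing makes an older participant's food alike across the two periods beyond a common sodium target and a 24-hour avoid-list, and the record that could do so has no stated use for it. The exposed part is Day 2 food water, on a day that carries 14 of 52 oz (27%) of the planned fluid contrast at 70 kg, plus sodium around its target.

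Unrelated differences add noise. Bias requires food choice to respond systematically to the condition, which is plausible but not shown. The conclusion assumes that the packets do not already ask for repeated foods. It does not call the crossover invalid or the 24-hour window wrong: that window roughly matches the day on which the full restriction applies.

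**What to change.** Add to section 6 and to both hydration packets:

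1. At study visit 1, give each older participant a copy of the period-1 three-day diet record.
2. Ask for the same foods on the matching days before visit 2. The 2,300 mg sodium target and the avoid-list continue to apply in both periods; any period-1 item that broke either is replaced, not copied.
3. At visit 2, check the second record against the first and note departures.

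Fluid allowances and the symptom safeguards in section 8 stay as they are. Do not extend the avoid-list to Day 2: that would lower total water intake for another day in a group that section 8 regards as possibly more prone to dehydration symptoms. Young adults have one study visit and are unaffected. If the packets already ask for repeated foods, one sentence in section 6 saying so is enough.

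The cost is a small amendment, one photocopy per older participant and a few minutes of checking. The downsides are slight participant burden, imperfect repetition, and the chance that a diet shaped by restriction in period 1 is carried into period 2.

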7. STUDY POPULATION AND RECRUITMENT

Describe who and how many subjects will be invited to participate. Include age, gender and other pertinent information.

An estimated 80 participants (40 young adults & 40 older adults) will be recruited to participate from the community surrounding the University of Delaware, Newark, DE. Participants will be recruited by flyers posted in different community locations. Also, flyers will be distributed to students in the department of Kinesiology & Applied Physiology via e-mail. We will IRB approved language from the informed consent, recruitment scripts, and flyers to recruit via UD classifieds, social media, postings in the Newark community, and at community events. The population being asked to participate are men and women between the ages of 20-35 and 55-75 years old with a body mass index (ratio of height and weight) score between 18.5 and 29.9. Also, participants must be non-smokers with blood pressures within specific limits (systolic 90-139 mmHg and diastolic blood pressure 50-89 mmHg) and have no known cardiovascular diseases, metabolic diseases, cancers, kidney diseases, and/or other chronic diseases. In addition, individuals that consume nicotine, are pregnant, plan on becoming pregnant, or currently receiving hormone replacement therapy do not qualify.

Attach all recruitment fliers, letters, or other recruitment materials to be used. If verbal recruitment will be used, please attach a script.

Describe what exclusionary criteria, if any will be applied.

- Outside the age ranges of 20-35 or 55-75
- Those with a body mass index score under 18.5 or over 29.9
- Smokers and nicotine users
- Resting blood pressure outside specific limits (those with systolic outside the range of 90-139 mmHg or diastolic outside the range of 50-89mmHg)
- Those who are pregnant, plan on becoming pregnant, or currently receiving hormone replacement therapy

Describe what (if any) conditions will result in PI termination of subject participation.

A person will be excluded for adverse side effects to the water restriction protocol, a positive pregnancy test, recent significant change in body weight or change in health status.

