8. RISKS AND BENEFITS

List all potential physical, psychological, social, financial or legal risks to subjects (risks listed here should be included on the consent form).

There are no known risks associated with obtaining consent, height, weight, a resting ECG, resting blood pressure, urine analysis or using ultrasound to measure blood flow.

Hydration Protocol

There are some risks when old participants are asked to limit water intake during the water restriction protocol. During the water restriction protocol participants may develop a dry mouth, develop thirst, become tired, develop a headache, develop constipation, or become dizzy or light headed. This protocol is designed to induce mild dehydration and we have identified strategies and remedies to prevent moderate to severe dehydration. First, participants will not be exercising prior to the water restriction therefore activity will not contribute to the mild dehydration. Second, participants will be told to swish water in their mouth and spit it out as needed to reduce thirst. If participants do begin to feel the more severe forms of dehydration (severe headache, extreme thirst, very dry mouth) they will be instructed to consume 8oz of water and if symptoms are not resolved within 30 minutes, participants will be instructed to consume another 8oz of water. We anticipate quick resolution of any dehydration related symptoms after the consumption of 8oz of water, however if symptoms are present after 30 minutes they will be instructed to contact the investigators and if necessary seek medical attention.

The technique of mild dehydration through short-term water restriction is an accepted and safe technique. Included is a list of five published papers where this technique has been used (1-5):

1. Armstrong, L. E., et al. "Thermal and Circulatory Responses during Exercise: Effects of Hypohydration, Dehydration, and Water Intake." *Journal of applied physiology* (Bethesda, Md.: 1985) 82.6 (1997): 2028-35. Print.
2. Charkoudian, N., et al. "Interactions of Plasma Osmolality with Arterial and Central Venous Pressures in Control of Sympathetic Activity and Heart Rate in Humans." *American journal of physiology. Heart and circulatory physiology* 289.6 (2005): H2456-60. Print.
3. Judelson, Daniel A., et al. "Effect of Hydration State on Strength, Power, and Resistance Exercise Performance." *Medicine and science in sports and exercise* 39.10 (2007): 1817. Print.

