In order to minimize risks, the heart rate and blood pressure will be monitored throughout testing. Should we see excessive blood pressure increases or heart rate irregularities, we will terminate the testing visit.

Hydration Protocol

Following the water restriction protocol data collection visit, participants will be told to consume water. If any symptoms of mild dehydration are present, we anticipate quick resolution after the consumption of 8-16oz of water. In the event that someone would require medical treatment, they will be referred to the Nurse Managed Primary Care Center.

As stated, there are potential risks associated with short term water restriction. In order to mitigate these risks and discomfort, they will be instructed to swish water in their mouth, refrain from strenuous exercise, and avoid hot environments for extended periods of time. If participants do begin to feel the more severe forms of dehydration (severe headache, extreme thirst, very dry mouth) they will be asked to consume 8oz of water and if symptoms are not resolved within 30 minutes, participants will be instructed to consume another 8oz of water. If symptoms persist, participants will be instructed to contact the investigators and if necessary seek medical attention.

Old adults may be more susceptible to dehydration related symptoms. We will monitor them closely during the dehydration protocol and instruct them to consume water if they begin to feel more severe symptoms of dehydration (listed above).

Catheter Insertion & Blood Draw

Standard safety precautions will be taken when drawing blood samples and placing IV catheters. To minimize the risk of infection associated with blood collection, only sterile, single use catheters will be used. To minimize the risk of bruising, proper blood collection technique will be utilized.

Tests of Sympathetic Reactivity

Participants will be re-assured that at any time during the protocol, if they feel too uncomfortable to continue than we will stop testing. Blood pressure will be continuously monitored during exercise. If there is an excessive increase in blood pressure, defined as systolic blood pressure above 220 mmHg or diastolic blood pressure above 110 mmHg, exercise will be terminated.

Isometric Handgrip Exercise and Post Exercise Ischemia Trial

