9. COMPENSATION

Will participants be compensated for participation?

Yes

If so, please include details.

Old adults:

\$150 for full completion of the research protocol (6 visits).

\$130 if they complete one of the two three-hour experimental visits, and not physical activity monitoring.

Young adults:

\$85 for full completion of the research protocol (4 visits).

\$65 if they complete one of the one three-hour experimental visits, and not physical activity monitoring.

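### Does an open-ended exclusion for side effects of water restriction, combined with payment tied to completed visits, make reporting symptoms costlier in one randomised order than in the other?

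*Protocol*

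**What the plan says.** Section 7, answering the form's question on when the investigator ends participation, says "A person will be excluded for adverse side effects to the water restriction protocol". It gives no symptom, grade or duration. The same sentence adds a positive pregnancy test, a recent significant weight change and a change in health status, the last of which is equally open.

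Section 8 deals with symptoms in two places. Under the hydration risks it lists the mild effects that may occur and offers a comfort measure: "participants will be told to swish water in their mouth and spit it out as needed to reduce thirst". For more severe symptoms it prescribes a drink of water and, if they have not resolved in half an hour, a second drink. It then says "We anticipate quick resolution of any dehydration related symptoms after the consumption of 8oz of water, however if symptoms are present after 30 minutes", the participant contacts the investigators. Under the steps to minimise risk the same sequence is repeated, ending with "another 8oz of water. If symptoms persist, participants will be instructed to contact the investigators".

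For old adults, Section 6 says "They will be assigned to a normal hydration and water restriction protocol for each of the two study visits, in a random order", and "we will schedule two study visits separated by one week".

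Section 9 lists two amounts for old adults: $150 "for full completion of the research protocol (6 visits)" and $130 "if they complete one of the two three-hour experimental visits, and not physical activity monitoring". No other case is priced.

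**The concern.** Restriction takes place at home, so the team learns of symptoms mainly from the participant. If any side effect can end participation, and listed payment starts only at a completed experimental visit, a participant has a financial reason to say nothing. Random order seems to make that reason unequal. Someone restricted first and stopped before the first experimental visit has no listed payment, while someone restricted second and stopped at the same stage has already reached the $130 tier. Section 8 itself says that old adults may be more susceptible to symptoms, and no listed visit falls within the restriction days. At stake would be the safety reporting on which Section 8 relies and, in principle, dropout from the crossover that differs by order.

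The contact step adds to the doubt. One description ties it to symptoms present after 30 minutes, in a sentence that mentions a single drink. The other places it after the second drink and gives no time.

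**Working it through.** **Payment by order.** Inputs from Section 9 (old adults): full completion $150; one experimental visit without monitoring $130. Amount forgone = $150 minus the amount paid at the stage reached.

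- Restriction second, stopped before that visit: 150 − 130 = $20, and 20/150 = 13.3%.
- Restriction first, stopped before that visit: 150 − x, where x is the payment to someone with no completed experimental visit. The protocol does not give x.

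The range below takes x as an assumption:

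| Assumed x | Forgone, restriction first | Forgone, restriction second | Gap between orders |
|---|---|---|---|
| $0 | $150 | $20 | $130 |
| $20 | $130 | $20 | $110 |
| $65 | $85 | $20 | $65 |
| $130 | $20 | $20 | $0 |

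The full $150 against $20 contrast is therefore the top row only.

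**Is the $20 figure secure?** Two points in the text weaken it.

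- The $130 tier applies only when activity monitoring has not been done. Section 6 allows monitoring between earlier visits where scheduling permits. A restriction-second participant who has already been monitored has no listed amount either.
- The old-adult step (150 − 130 = $20) equals the young-adult step for monitoring alone (85 − 65 = $20), and the young-adult line has garbled wording about one visit out of one. The $130 may have been meant for both experimental visits without monitoring. If so, a single visit is not priced, people stopped before the restriction visit have no listed amount in either order, and the gap between orders on listed amounts is nil.

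**Time already given.** From Section 6: consent 0.5 h + screening 1 h + familiarization 0.5 h = 2.0 h over 3 visits. Adding one 3 h study visit gives 5.0 h over 4 visits. Adding the second study visit and the accelerometer return (at most 5 minutes) gives about 8.1 h over 6 visits, which matches the stated total of about 8 hours. The visit counts behind the concern are therefore right.

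**Exclusion rule against symptom management.** Section 7 names a category of reasons for termination. Section 8 describes what is done about symptoms: mild ones are expected and tolerated, severe ones are met with water, then contact with the investigators, then medical attention if necessary. Nothing in Section 8 says that a person with severe symptoms must continue, and nothing in Section 7 says that every expected symptom ends participation. Read together, they give graded management with the decision to stop left to the investigator.

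**Contact step.** Set side by side:

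- Hydration risks: 8 oz; 30 minutes; another 8 oz; contact if symptoms are present after 30 minutes.
- Steps to minimise risk: 8 oz; 30 minutes; another 8 oz; contact if symptoms persist.

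Taken alone, the first version's last sentence could mean 30 minutes after the first drink, or 30 + 30 = 60 minutes if counted from the second. The 60-minute figure appears nowhere in the protocol. Read in sequence, both versions put contact after the second drink.

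**Effect on the comparison.** A participant stopped before the restriction visit contributes no complete pair in either order. The protocol gives no exclusion or non-reporting rate, so no bias can be computed.

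**The case for a change.** The strongest argument for acting is that the rule in Section 7 is phrased as mandatory and, taken literally, would exclude people for the thirst and dry mouth that the intervention is designed to produce. Section 9 is where payment details are requested, and it is silent about the participants most exposed to that rule. The protocol rates its own risk as more than minimal, partly because of water restriction in old adults; it has no data monitoring committee; and it promises close monitoring without saying how. Wording that settled the matter would cost little.

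Part of this stands. The silences are real, and an investigator or ethics office might reasonably tidy them. The incentive argument needs more than silence, though. Participants would have to know of the exclusion rule and believe that reporting ends their payment. What they are told is in the old-adult consent form and the water restriction packet, both listed in Section 15 and neither available here. The first responses to severe symptoms, the two drinks, are taken by the participant and do not depend on making a report. Any payment tied to completion creates some incentive of this kind. The order-dependent part is also confined to a short window: in the 70 kg example, Day 1 intake is 54 oz in both conditions, so the conditions differ only on Days 2 and 3 and the morning of the visit.

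**Conclusion.** The concern does not hold as a fault in the plan. The quotations and subtractions are correct, but dependence on randomised order follows only if nothing is paid before the first experimental visit and the $130 tier is read literally. The protocol does not state the first, and its own figures cast doubt on the second. Across the assumed payments the gap between orders runs from $130 to nil.

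What is left is ordinary missing detail: no threshold in a termination category that investigators apply by judgement, no listed payment for one administrative case, and a loosely worded contact sentence that fits the fuller version. The text does not show a rule that gives a wrong result, and no effect on the blood pressure estimate can be derived. This conclusion takes no view on which symptoms should end participation or when contact should be made. It would need another look if the consent form or the restriction packet told participants that reporting symptoms forfeits payment for visits already made.
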